#### 9. PATIENT SELECTION

Effective 20 January 2021, no new subjects can be enrolled in the study.

# 9.1. Inclusion Criteria

To be included in the study, subjects must meet the following criteria:

- 1. Male or female and at least 4 years of age at time of screening.
- 2. Has a confirmed diagnosis of NPC and exhibits neurologic symptoms.
- 3. Patient or parent/guardian must provide written informed consent to participate in the study. In addition to parental consent, assent to participate must also be sought from minor children.
- 4. Has the ability to undergo LP and IT drug administration.
- 5. If taking miglustat (Zavesca®), must have been on a stable dose for the past 6 weeks and be willing to remain on a stable dose for the duration of participation in the study. Alternatively, subjects may elect to discontinue miglustat use and be eligible for entry into the study after undergoing a minimum 6-week washout period prior to study Day 1.
- 6. If there is a history of seizures, the condition must be adequately controlled, ie, the pattern of seizure activity must be stable and the subject must be on a stable dose and regimen of antiepileptic medication during the 1 month prior to Screening, with no change in dose or regimen up to and including the day of the first dose of adrabetadex (Day 1).
- 7. If not currently receiving adrabetadex, agrees to discontinue any other investigational treatments for at least 1 month prior to first dose of adrabetadex (Day 1); subjects who are currently receiving intrathecal adrabetadex are eligible to participate.
- 8. Sexually active females and males must use a medically acceptable method of contraception and must agree to continue use of this method for the duration of the study and for 30 days after participation in the study. Acceptable methods of contraception include barrier method with spermicide, intrauterine device, steroidal contraceptive in conjunction with a barrier method, abstinence, or same-sex partner.
- 9. Patient or parent/guardian must possess the ability, in the clinician's opinion, to understand and comply with study requirements, including clinical outcome measurements and instructions, for the entire duration of the study.
- 10. Caregiver, parent, guardian, or responsible adult must be able and willing to accompany the subject to study visits.

#### 9.2. Exclusion Criteria

Patients will be excluded from the study if they meet any of the following criteria:

- 1. Weighs less than 15 kg.
- 2. Has uncontrolled psychosis.

- 3. Has a history of hypersensitivity reactions to any product containing HP-β-CD or has a history of hypersensitivity reactions or allergy to anesthesia/sedation.
- 4. Has received treatment with any investigational product (other than adrabetadex) within 1 month prior to Day 1 of treatment.
- 5. Is a female who is pregnant or nursing.
- 6. Has suspected infection of the CNS or any systemic infection.
- 7. Has a spinal deformity that, in the opinion of the clinician, could impact the ability to perform repeated LPs.
- 8. In the opinion of the clinician, has a serious skin infection in the lumbar region within 2 months of entry into the study.
- 9. Has neutropenia, defined as an absolute neutrophil count of less than  $1.0 \times 10^9$ /L.
- 10. Has thrombocytopenia (platelet count of less than  $75 \times 10^9$ /L).
- 11. Has an activated partial thromboplastin time (aPTT) or prothrombin time (PT) prolonged by greater than 1.5 times the upper limit of normal (ULN) or a known history of a bleeding disorder.
- 12. Has evidence of obstructive hydrocephalus or normal pressure hydrocephalus.
- 13. Has recently used anticoagulants (in past 2 weeks prior to first dose of adrabetadex [Day 1]).
- 14. In the opinion of the clinician, is unable to comply with the study or has a medical condition (eg, cardiovascular, respiratory, hematologic, neurologic, renal) that would potentially increase the risk of participation.

# 10. CONCOMITANT MEDICATIONS

Any changes to medications should be noted in the subject's medical record/source documents. Concomitant medications must be added to the appropriate case report form (CRF).

Use of anticoagulants is prohibited during the study. The use of other investigational medications and treatments is also prohibited. (If a clinician has any questions about whether a medication is allowed or prohibited, he/she should contact the medical monitor).

# 11. TREATMENTS

# 11.1. Method of Assigning Patients to Treatment Groups

Effective 20 January 2021, no new subjects can be enrolled in the study.

# 11.2. Blinding

This is an open-label study.

#### 11.3. Test and Control Product

Adrabetadex will be provided in appropriately labeled vials, formulated as a 200 mg/mL injectable solution. A pharmacist/designee at each study site will be responsible for dispensing or preparing the assigned dosage. The 400 mg dose will be administered in 2 mL of solution; a 600 mg dose will be administered in 3 mL of solution, and a 900 mg dose will be administered in 4.5 mL of solution. The total infusion volume should be 10 mL; to achieve a final total volume of 10 mL, 0.9% sterile sodium chloride for injection, USP should be added to the adrabetadex solution. Doses other than those provided in the examples above will be prepared in the same manner.

No control product will be used in the study.

#### 11.3.1. Formulation of Test Product

The formulation and filling of adrabetadex involves dissolving the Active Pharmaceutical Ingredient in water for injection, adding sodium chloride to 0.9% weight/volume (w/v) and adjusting the pH if necessary with sodium hydroxide or hydrochloric acid, and bringing to the final volume with water for injection. The product is then filled into vials (4.5 mL fill with sufficient overfill to allow product withdrawal) and autoclaved. The product is a clear, colorless solution that is free from visible foreign matter.

#### 11.3.2. Packaging and Labeling

Preparation, packaging, and labeling of all study drugs will be in accordance with standard operating procedures, Good Manufacturing Practice (GMP) guidelines, International Council for Harmonisation (ICH) Good Clinical Practice (GCP) guidelines, and applicable local laws/regulations. All investigational drug used in this study will be prepared, packaged, and labeled under the responsibility of the sponsor and its designees. Refer to the Pharmacy Manual for information on packaging and labeling.

# 11.3.3. Supply of Investigational Drug at the Site

The sponsor (or designee) will ship adrabetadex to the study sites. The initial adrabetadex shipment will occur after site activation (ie, all required regulatory documentation has been received by the sponsor or designee, and a contract has been executed). Subsequent adrabetadex shipments will be made after site request for resupply. Instructions for ordering, preparing, and handling study drug are provided in the Pharmacy Manual.

## 11.3.4. Dispensing

A pharmacist/designee at each study site will be responsible for preparing the assigned dosage in a sterile environment (eg, under a laminar airflow hood or other clean room environment). Alternatively, the pharmacist/designee may dispense the assigned dosage for subsequent preparation by the IT administrator within the sterile field of the LP procedure room.

# 11.3.5. Storage

Investigational product should be stored between 15 and 25°C (59-77°F), inclusive. The pharmacy/designee is responsible for the secure and temperature-controlled storage of adrabetadex. This includes daily documentation of the storage and temperature conditions of adrabetadex as described in the Pharmacy Manual.

#### 11.3.6. Investigational Drug Accountability

Drug supply will be managed by a designee at the site and the pharmacy/designee will maintain an accountability log for adrabetadex. The clinician is responsible for the accountability of the investigational product. This will include documentation of receipt, storage, and dispensing of adrabetadex. The clinician will return or destroy (per instruction of sponsor or designee) unused investigational drug at the conclusion of the study.

# 11.4. Dosage/Dosing Regimen

Adrabetadex will be provided in labeled 10 mL Type I glass vials, formulated as a 200 mg/mL injectable solution (4.5 mL fill with overfill). Examples of how the assigned dosage will be administered are provided in Table 1.

The total infusion volume should be 10 mL; to achieve a final total volume of 10 mL, 0.9% sterile sodium chloride for injection, USP should be added to the adrabetadex solution (eg, add 8 mL of 0.9% sodium chloride to 400 mg dose).

Adrabetadex administration via LP will be conducted every 2 weeks. Sedation or anesthesia may be used as indicated by the clinical condition of the subject. Sedation and anesthesia will follow institutional guidelines and procedures. Ultrasound or other imaging techniques may be used to guide IT administration of adrabetadex.

Treatment with adrabetadex will continue until the clinician considers adrabetadex to be no longer beneficial to the subject, the subject withdraws from the study, adrabetadex receives marketing authorization in the US, or the development program is discontinued. There are no adjustments of dosing regimen for weight or subject age. Patients participating in this study should not expect additional access to adrabetadex beyond this study.

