# 4. SYNOPSIS

Title	Open-label Evaluation of Adrabetadex in Patients with Neurologic Manifestations of Niemann-Pick Type C Disease (NPC)		
Sponsor	Vtesse LLC, a Mallinckrodt Pharmaceuticals Company		
Number of Patients and Sites	Approximately 60 subjects at 30 sites in the United States (US)		
Study Design	No new subjects can be enrolled in the study effective 20 January 2021.		
	This is a prospective, open-label study to evaluate the safety of adrabetadex in subjects with neurologic symptoms of Niemann-Pick type C disease (NPC). Eligible subjects will receive adrabetadex intrathecally (IT) via lumbar puncture (LP) every 2 weeks, and assessments of safety measures will be performed at prescribed intervals. Patients who had not previously been treated with adrabetadex will start at a dose of 400 mg, and subjects who had been previously receiving adrabetadex will receive their current stable dose of adrabetadex. Following a determination of a negative benefit/risk balance by the Sponsor, treatment will be allowed to continue up to 20 October 2021. Continuation of treatment is contingent upon reconsent by the subject/legally acceptable representative as well as approval by the Institutional Review Board (IRB)/Ethics Committee (EC) and Food and Drug Administration (FDA).		
Dose Adjustment	Effective as of the date of Amendment 2 (21 April 2021), subjects will remain at their current dose or their dose may be decreased for tolerability reasons. A subject's dose may not be increased.		
Objectives	Primary and secondary objectives and endpoint	ts are presented in the table below.	
	Primary Objectives	Primary Endpoints	
	To evaluate the longer-term safety and tolerability of adrabetadex administered IT via LP every 2 weeks	Summary of TEAEs, SAEs, discontinuation due to TEAEs, and deaths	
	Secondary Objectives	Secondary Endpoints	
	To summarize additional longer-term safety and tolerability of adrabetadex administered IT via LP every 2 weeks	
 
Change in audiologic testing.
 
Laboratory changes from baseline (hematology, chemistry, coagulation,
 
	
		urinalysis.)	
		Vital sign measurements.	
		Physical and neurological examination.	
	IT=intrathecal(ly); LP=lumbar puncture; SAE=serious adverse event; TEAE=treatment-emergent adverse event		

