# Duration of Patient Participation

Effective 20 January 2021, Mallinckrodt is recommending that treatment with adrabetadex be discontinued as soon as possible with appropriate clinician oversight.

In recognition of the complexity of patient care, Mallinckrodt will make adrabetadex available for up to 9 months to allow time for the physician and subject/family to develop a transition plan. Continued treatment with adrabetadex is contingent upon a discussion between the treating physician and subject/family and re-consent. Likewise, continuation of treatment is also contingent upon approval by the respective IRB/Ethics Committee (EC) and health authority.

After 21 June 2021 subjects may not continue to receive intrathecal adrabetadex, except for those subjects (and legally authorized representatives, as appropriate):

- who appear to be benefiting from intrathecal adrabetadex based on the investigator's assessment, AND
- who are aware of the risks associated with adrabetadex, including hearing loss, and understand that no significant differences were seen between subjects treated with

	adrabetadex and sham-treated subjects on any efficacy measures in this randomized, controlled trial.	
Primary Safety Evaluations	Summary of TEAEs, SAEs, discontinuation due to TEAEs, and deaths	
Secondary Safety Evaluations	
 
Changes in audiologic testing
 
Laboratory changes from baseline (hematology, chemistry, coagulation, urinalysis)
 
Vital sign measurements
 
Physical and neurological examination.
 
	
Statistics	Data from the study will be summarized using descriptive statistics. No hypothesis testing will be conducted.	
Date	23 June 2021	

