#### 15. DISCONTINUATION AND REPLACEMENT OF PATIENTS

# **15.1.** Early Discontinuation

A subject may be discontinued from study treatment at any time if the subject, the investigator, or the sponsor feels that it is not in the subject's best interest to continue.

The sponsor has made a determination of a negative benefit/risk balance for adrabetadex. Subjects in this study will be allowed to continue treatment until 20 October 2021 to allow time to start alternative treatment unless there are additional time restrictions mandated by an IRB/EC or health authority.

After 21 June 2021, subjects must be discontinued from the study if the investigator does not consider them to be benefiting from treatment and/or they do not understand the risks associated with adrabetadex, including hearing loss, and that the data from the randomized, controlled trial did not demonstrate significant differences between subjects treated with adrabetadex and shamtreated subjects on any efficacy measures. This discussion should be documented in the subject's medical record and only those subjects (or legally authorized representative) who have demonstrated an understanding of the risk/benefit of adrabetadex treatment should be permitted to continue in the study.

Following the last dose of adrabetadex, subjects will be asked to return to the clinic for a follow-up safety visit. Procedures for the End of Study visit and the safety follow-up visit are noted in Table 5.

If a subject is withdrawn from treatment due to an AE, the subject will be followed and treated by the clinician until the abnormal parameter or symptom has resolved or stabilized.

Reasonable attempts will be made by the clinician to provide a reason for subject withdrawals. The reason for the subject's withdrawal from the study will be specified in the subject's source documents.

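### Section 11.4's treatment-duration rule conflicts with the Synopsis and Section 15.1 in two cases: benefit after 20 October 2021, and benefit without understanding of the risks after 21 June 2021

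*Combined protocol and SAP*

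**What the plan says.** Three places in the protocol say how long treatment lasts.

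- **Section 11.4 (Dosage/Dosing Regimen).** "Treatment with adrabetadex will continue until the clinician considers adrabetadex to be no longer beneficial to the subject", or until the subject withdraws, "adrabetadex receives marketing authorization in the US, or the development program is discontinued". There is no calendar date, no condition about understanding the risks, and no cross-reference to Section 15.1.
- **Synopsis.** Under Study Design: "treatment will be allowed to continue up to 20 October 2021". Under Duration of Patient Participation: "After 21 June 2021 subjects may not continue to receive intrathecal adrabetadex, except for those subjects" who meet two conditions joined by AND. The first is apparent benefit in the investigator's assessment. The second is awareness of the risks, including hearing loss, together with an understanding that the randomized trial showed no significant difference from sham on efficacy.
- **Section 15.1 (Early Discontinuation).** "Subjects in this study will be allowed to continue treatment until 20 October 2021", unless an ethics board or health authority sets a tighter limit. After 21 June 2021 it makes discontinuation mandatory if either the benefit or the understanding is missing.

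Sections 7.3 and 13 repeat the two conditions. The Synopsis dates the protocol 23 June 2021, two days after the date from which the conditions apply.

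**The concern.** Section 11.4 is current body text, not a change log, so it cannot be set aside as superseded. It is worded as a rule on how long treatment goes on, and that rule differs from the one in the Synopsis and Section 15.1. The list of sections touched by Amendment 3 names the Synopsis and Sections 7.3, 13 and 15.1, but not 11.4. Other sections, such as 9, 11.1 and 12.2.6, carry dated restrictions. Section 11.4 looks like text that was not updated.

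The stakes are practical. The sponsor has declared the benefit/risk balance negative (Sections 5 and 15.1), and Section 7.3 expects some irreversible hearing loss. Section 16 counts certain failures to follow the protocol as major deviations. A site or monitor judging a late dose, or a dose to a subject who does not meet the second condition, needs one rule to judge it against.

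**Working it through.** **Step 1: do the dated passages agree with each other?**
The Synopsis says "Effective 20 January 2021, Mallinckrodt is recommending that treatment with adrabetadex be discontinued as soon as possible", and then "Mallinckrodt will make adrabetadex available for up to 9 months". Section 5 says the same. Reading the nine months as running from 20 January 2021:

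20 January 2021 + 9 calendar months = 20 October 2021 (273 days).

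This reproduces the date in the Synopsis and Section 15.1. Those passages are consistent with one another, and Section 11.4 is the one that differs.

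**Step 2: where do the two rules give different answers?**

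| Period | Subject | Section 11.4 | Synopsis and Section 15.1 | Conflict? |
|---|---|---|---|---|
| After 21 June, to 20 October 2021 | Judged to benefit, understands the risks | Continues | May continue | No |
| Same | Judged not to benefit | Stops | Stops | No |
| Same | Judged to benefit, does not understand the risks | Continues | Stops | **Yes** |
| After 20 October 2021 | Still judged to benefit | Continues | Stops | **Yes** |
| Same | Judged not to benefit | Stops | Stops | No |

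The benefit condition overlaps with the first end point in Section 11.4. Before 20 October the conflict is therefore confined to the third row.

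**Step 3: how long can the conflict last for one subject in the third row?**

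- 21 June to 20 October 2021: 9 + 31 + 31 + 30 + 20 = 121 days.
- Dosing is every 2 weeks: 121 / 14 = 8.6 intervals.

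This is a maximum for one subject in that row. It is not a count of infusions for every subject. The documents give no figure for how many subjects are in either conflicting row.

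**Step 4: does the analysis depend on it?**
Section 18 defines treatment-emergent events by Day 1 and the treatment period, and refers to neither Section 11.4 nor 15.1. Sections 12.2.2 and 14.2.1 collect adverse events to Follow-up Visit 3 whatever the reason for stopping. Section 18 plans descriptive summaries on available data and no analysis of exposure time. No planned output changes with the choice of duration rule.

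**The case against.** The best defence is that Section 11.4 was never a complete list. It also leaves out pregnancy (Section 14.2.3), intolerance of the lowest dose (Section 7.2) and discontinuation at the sponsor's or investigator's discretion (Section 15.1), and nobody would read it as overriding those. On this view its silence on the end date and on understanding is omission, not contradiction. Much of this stands. A careful site would probably follow the dated text, and the sponsor controls supply (Section 11.3.3). A reader might infer that Section 11.4 opens the way to unlimited dosing after October. The documents do not support that, because it lists four limits of its own and the supply is stated to be time-limited. But Section 11.4 does set out to say when treatment ends, and on that subject it says something different.

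A second defence is that program discontinuation, one of the Section 11.4 end points, covers the sponsor's decision. The documents never say that the program is discontinued on 20 October 2021, and Section 5 still describes the drug as in development. If the January 2021 determination counted as discontinuation, Section 11.4 would have ended treatment then, against the nine-month transition. If it did not count, Section 11.4 has no calendar end. Neither reading supplies the condition on understanding.

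Two further inferences are tempting and fail. One is that 8 to 9 infusions per subject are in conflict; the table shows that most combinations give the same answer under both rules. The other is that the window for treatment-emergent events, or exposure time, acquires two end points; step 4 shows that the plan does not use the duration rule in that way.

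**Conclusion.** The point holds as an internal inconsistency in current text, limited to the two conflicting rows. For the case after 20 October the disagreement is direct. For the case between June and October it turns on the second condition alone, and may be rare, since a legally authorized representative can show the understanding on the subject's behalf. The bound of 8 to 9 intervals assumes the two-weekly schedule throughout, and reads the period as running from 21 June to 20 October. The ±1 week visit windows could shift individual doses. No sample size, power or error rate is involved, because the study tests no hypothesis. The correction should be made because the texts disagree on when to stop a drug whose benefit/risk balance the sponsor calls negative. It is not a flaw in the statistical analysis.

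**What to change.** The sponsor must reconcile Section 11.4 with Section 15.1 and the Synopsis so that a single treatment-duration rule applies throughout, for example by stating it once and cross-referring to it elsewhere. Which rule applies is for the sponsor and its clinical advisers, and none is proposed here. Section 18 needs no change. The length of permitted treatment is not the date on which a given subject stopped, so the analysis window should not be tied to it. The cost is amendment wording and the usual ethics board submission, with no new data, visits or analyses.

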# 11.5. Adrabetadex Administration by Lumbar Puncture

Adrabetadex will be administered as an IT slow bolus (1 to 2 minutes, depending on the volume administered) LP injection (maximum rate of administration = 4.5 mL/minute). The volume of the injection will be approximately 10 mL (Table 1). Prior to the adrabetadex injection, a volume of cerebrospinal fluid approximately equal to the infusion volume is to be removed. Anesthesia or sedation will be used for the IT dosing procedure, following institutional guidelines and

procedures. Patients will be required, if possible, to lie flat for 30 to 45 minutes following dosing with feet elevated. For the 3 days following each procedure, subjects should avoid acoustic overstimulation and minimize exposure to loud noises, eg, headphones for music or video games.

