#### Test and Control Product, Dose, and Route of Administration

Adrabetadex will be provided in appropriately labeled vials, formulated as a 200 mg/mL injectable solution. A pharmacist/designee at each site will be responsible for dispensing or preparing the assigned dosage: 400 mg in 2 mL of solution, 600 mg in 3 mL of solution, or 900 mg in 4.5 mL of solution. The total infusion volume should be 10 mL; to achieve a final total volume of 10 mL, 0.9% sterile sodium chloride for injection, USP should be added to the adrabetadex solution. Doses other than 400 mg, 600 mg or 900 mg will be prepared in the same manner.

Adrabetadex administration via LP will be conducted every 2 weeks. Sedation or anesthesia may be used as indicated by the clinical condition of the subject. Sedation and anesthesia will follow institutional guidelines and procedures. Ultrasound or other imaging techniques may be used to guide IT administration of adrabetadex.

Adrabetadex will be administered as an IT slow bolus (1 to 2 minutes, depending on the volume administered) LP injection (maximum rate of administration = 4.5 mL/minute). Prior to the adrabetadex injection, a volume of cerebrospinal fluid approximately equal to the infusion volume (approximately 10 mL) will be removed.

Patients will be required, if possible, to lie flat with feet elevated for 30 to 45 minutes following dosing. For the 3 days following each procedure, subjects should avoid acoustic overstimulation and minimize exposure to loud noises, eg, headphones for music or video games.

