**Table 1: Adrabetadex Dose and Infusion Volume** 

Dose Group a	Adrabetadex Volume	Volume of 0.9% NaCL	Total Infusion Volume
400 mg	2.0 mL	8 mL	10 mL
600 mg	3.0 mL	7 mL	10 mL
900 mg	4.5 mL	5.5 mL	10 mL

<sup>a Doses other than those provided in the examples above will be prepared in the same manner. NaCL = sodium chloride.

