# 11.6. Measures of Treatment Compliance

Adrabetadex will be administered at the clinical site by a study clinician, and the amount of drug infused will be recorded in the dose preparation worksheet and maintained in the subject's medical record/source documents.

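### A 10 mL intrathecal dose cannot be given in the stated 1 to 2 minutes without exceeding the stated maximum of 4.5 mL/minute; at that rate it needs at least 133 seconds

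*Combined protocol and SAP*

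**What the plan says.** Section 11.5 gives the duration and the rate limit together: "IT slow bolus (1 to 2 minutes, depending on the volume administered) LP injection (maximum rate of administration = 4.5 mL/minute"). Its next sentence gives the volume: "The volume of the injection will be approximately 10 mL (Table 1"). The Synopsis, under the test product and route of administration, has the same duration ("Adrabetadex will be administered as an IT slow bolus (1 to 2 minutes, depending on the volume administered) LP injection") and the same limit. It sizes the fluid withdrawal to match: "a volume of cerebrospinal fluid approximately equal to the infusion volume (approximately 10 mL) will be removed".

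The volume is fixed elsewhere too. Section 11.3 states "The total infusion volume should be 10 mL", and Section 11.4 repeats it. Table 1 shows a 10 mL total for 400, 600 and 900 mg, made up of 2.0, 3.0 or 4.5 mL of drug solution and the balance in saline. Its footnote covers any other dose: "Doses other than those provided in the examples above will be prepared in the same manner".

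On records, Section 11.6 says "the amount of drug infused will be recorded in the dose preparation worksheet". It does not ask for the time taken to inject. On the period still to run, Section 15.1 says "Subjects in this study will be allowed to continue treatment until 20 October 2021".

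**The concern.** Volume, duration and maximum rate are tied together by one equation, so any two determine the third. Here the three values do not agree at any point in the stated time range. An operator giving the full 10 mL must either inject faster than the maximum or take longer than the stated time. The only other way to satisfy both figures is to stop short of the full volume. The protocol does not say which instruction takes priority.

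What is at stake is whether an intrathecal dosing instruction can be followed as written. Because injection time is not a required record, a rate above the limit could pass unnoticed. The statistical analysis is not at stake: Section 18 plans descriptive summaries only, and no figure in them depends on injection rate.

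**Working it through.** **Inputs**

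- Volume: V = 10 mL (Synopsis; Sections 11.3, 11.4 and 11.5; Table 1)
- Duration: t = 1 to 2 minutes (Synopsis; Section 11.5)
- Maximum rate: R = 4.5 mL/minute (Synopsis; Section 11.5)
- Date of this version: 23 June 2021 (Synopsis)
- Last permitted treatment date: 20 October 2021 (Section 15.1)

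**Rate implied by the stated duration (V/t)**

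- At 1 minute: 10/1 = 10.0 mL/minute; 10.0/4.5 = 2.22, or 122% above the maximum.
- At 2 minutes: 10/2 = 5.0 mL/minute; 5.0/4.5 = 1.111, or 0.5 mL/minute (11%) above the maximum.

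The 2-minute end is the most favourable point in the range, and it still exceeds the limit.

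**Time implied by the stated maximum (V/R)**

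10/4.5 = 2.222 minutes = 133.3 s, which is 13.3 s longer than the 2-minute upper end.

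**Largest volume that satisfies both figures (R × t)**

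4.5 × 2 = 9.0 mL, or 90% of the prepared volume.

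**Does the word *approximately* in Section 11.5 close the gap?** The documents give no tolerance, so I assume a range of 9 to 10.5 mL:

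| Volume (mL) | Minimum time at 4.5 mL/minute (s) | Rate over 2 minutes (mL/minute) |
|---|---|---|
| 9.0 | 120.0 | 4.50 |
| 9.5 | 126.7 | 4.75 |
| 10.0 | 133.3 | 5.00 |
| 10.5 | 140.0 | 5.25 |

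Only 9.0 mL or less fits. If a site stopped at 2 minutes while holding to the limit (a hypothetical case, which nothing in the text instructs), it would deliver 0.9 × 400 = 360 mg, 0.9 × 600 = 540 mg or 0.9 × 900 = 810 mg. The shortfall would be 40, 60 or 90 mg.

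**Does the limit fit the undiluted drug?** The 900 mg dose contains 4.5 mL of drug solution, and 4.5 mL over 1 minute is exactly 4.5 mL/minute. The figures agree on that reading, but the text does not state it, and Section 11.5 gives the injected volume as about 10 mL.

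**Remaining exposure**

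23 June to 20 October 2021 is 7 + 31 + 31 + 30 + 20 = 119 days, or 17 weeks. 119/14 = 8.5 intervals, so at most 9 doses per continuing subject at nominal 2-week spacing, counting one on 23 June.

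**Check of the proposed wording**

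2 min 15 s = 2.25 minutes; 10/2.25 = 4.44 mL/minute, which is within the limit.

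**The case against.** The strongest reply is that a maximum is a hard limit, whereas the 1 to 2 minutes only describes a slow bolus and is itself qualified by volume. A clinician who lets the limit govern injects for about 2 min 13 s, gives the full dose and does no harm. The gap is 13 s on a hand-given injection. The documents attribute drug-related hearing loss to dose or duration of dosing (Section 5) and to infusion at a given dose (Section 14.1.8), never to injection speed. Under-delivery is unlikely: the amount infused is recorded, and Section 16 makes an incorrect dose a major deviation. Enrolment is closed, treatment ends within months, and a wording change goes to the IRB of each participating site, with about 30 sites planned. The wording may also be left over from an undiluted injection, in which case the documents cannot show which figure is wrong.

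Much of this stands. A compliant reading exists, no harm from speed is shown, and the shortfall figures are conditional. Which number is the error cannot be settled from the text, so the fix has to leave room for the sponsor to justify another limit. What does not stand is the idea that the text already resolves the conflict. The dependence on volume has no effect when every dose is 10 mL, and the compliant reading requires the operator to depart from the stated duration without being told to.

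**Conclusion.** The point holds. No time within the stated range delivers 10 mL at or below the stated maximum. At best the excess is 0.5 mL/minute (11%), or equivalently 13 s; at the 1-minute end the rate is 122% above the limit. This rests on two readings: that the limit applies to the diluted solution actually injected, and that the full 10 mL is given. Both are the plain sense of Section 11.5 and Table 1.

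The size is modest. The instruction now applies only to the restricted group allowed to continue after 21 June 2021, whose number the documents do not give, for at most 9 doses each. It should be fixed because an operative intrathecal dosing rule contradicts itself, not because any effect on safety results or on the analysis has been shown. The Pharmacy Manual was not available and might address this, but the protocol text would still need to agree with it.

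**What to change.** Keep 4.5 mL/minute as the governing limit unless the sponsor's clinical and pharmacy team justifies a higher one for the diluted 10 mL injection. Keeping a 2-minute injection would require a limit of at least 5.0 mL/minute. In the Synopsis and Section 11.5, replace the 1 to 2 minute duration and its volume qualifier with *over at least about 2 min 15 s for 10 mL*. Tell sites by letter.

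Injection duration can be added to the existing dose preparation worksheet for future doses. Past rates may not be recoverable, since Section 11.6 requires only the amount infused.

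The cost is one phrase in two places, a site letter, and IRB submission under Sections 20.1 and 20.2. That review across sites is the main burden, and the time it takes will reduce the number of doses that benefit. Each injection takes about 15 s longer than the current 2-minute end. No subjects, visits or procedures are added.
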